12.4.4.3 Reporting Device Deficiencies

A device deficiency is defined as an inadequacy of a medical device with respect to its identity, quality, durability, reliability, safety or performance. Device deficiencies include malfunctions, use errors, and inadequate labeling. All device deficiencies will be reported to the Sponsor and its representatives on a Device Deficiency Report form.

Investigators must evaluate, record, and report via applicable forms any complaints/deficiencies, or malfunctions that could potentially lead to a SAE during this trial to the Sponsor and its representative without unjustified delay. As required, such reports may be provided to the reviewing IRB per their established reporting procedures and the

FDA by the Investigator. Upon the Sponsor's request, Investigators must supply any additional information related to the safety reporting of a particular event.

The contact for reporting device deficiencies is:

The Sponsor shall review all device deficiencies and determine and document in writing whether they could have led to a SAE. In the event of a disagreement between the Sponsor and the Investigator(s), the Sponsor shall communicate both opinions to the reviewing IRB per their established reporting procedures and the FDA as described in **Table 4**.

12.4.5 Adverse Events and Unanticipated Adverse Device Effects at Subject Exit

Ongoing AEs will be followed until resolution; no further change in the condition is expected; as dictated by standard of care; or up to 30 days post final visit, whichever is shorter. Documentation in the CRFs of such follow-up is not required although subject care should continue as appropriate.

Ongoing UADEs will be followed by the Sponsor and its representative(s) and Investigator until their medical endpoints are determined or until no further change in the condition is expected.

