12.1 Evaluation of Safety

The primary safety variable will be the proportion of subjects who experience at least one IOP measurement ≥ 30 mmHg at any follow-up visit.

Secondary safety variables will be:

- Mean change from baseline in IOP at the six hour post-operative visit
- Mean change from baseline in IOP at the 24 hour post-operative visit

The incidence and type of AEs reported by the subject or observed by the Investigator at each study visit will be collected from the time the subject signs the ICF until study exit.

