12.4.1 Adverse Events Definitions

For the purposes of this study, adverse events include: ocular adverse events (AEs) in the study eye only; all ocular and non-ocular serious adverse events (SAEs); adverse device effects (ADEs); and unanticipated adverse device effects (UADEs). AEs, SAEs, ADEs and UADEs are defined as follows:

- Adverse Event (AE): any untoward medical occurrence, unintended disease or injury, or untoward clinical signs (including abnormal laboratory findings) in a subject, user or other persons, whether or not related to the investigational medical device. This definition includes events related to the investigational medical device, comparator or the procedures involved. For users or other persons, this definition is restricted to events related to investigational medical devices.
- Adverse Device Effect (ADE): an adverse event related to the use of an investigational medical device. This definition includes AEs resulting from insufficient or inadequate instructions for use; deployment, implantation, installation, or operation; or any malfunction of the investigational medical device. This definition also includes any event resulting from use error or from intentional misuse of the investigational medical device.
- Serious Adverse Event (SAE) is an AE that:
 - led to death;
 - led to serious deterioration in the health of the subject, that resulted in:
 - a life-threatening illness or injury; or
 - a permanent impairment of a body structure or a body function (e.g., blindness); or
 - in-patient or prolonged hospitalization; or
 - medical or surgical intervention to prevent life-threatening illness or injury or permanent impairment to a body structure or a body function;
 - led to fetal distress, fetal death, or a congenital abnormality or birth defect.

NOTE: Planned hospitalization for a pre-existing condition, or a procedure required by the protocol, without serious deterioration in health, is not considered a serious adverse event.
- Unanticipated Adverse Device Effect (UADE): any serious adverse effect on health or safety or any-life threatening problem or death caused by, or associated with a device, if that effect, problem or death was not previously identified in nature, severity or degree of incidence in the investigational plan or application (including a supplementary plan or application), or any other unanticipated serious problem associated with a device that relates to the rights, safety, or welfare of subjects.

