Experience with cataract surgery and the implantation of IOLs has shown that some adverse effects can be associated with either the surgical procedure or the lens implanted. The following is a non-inclusive list of anticipated ADEs which have the potential of being considered as SAEs should the circumstances meet the necessary SAE criteria:

- Corneal stromal edema
- Cystoid macular edema

- Wound leak (positive Seidel)
- Flat anterior chamber
- Iris prolapse
- Vitreous in anterior chamber
- Vitreous to wound
- Synechiae/ Fibrin in pupil
- Iritis
- Raised IOP requiring treatment
- Retained lens material
- Capsulorhexis tear
- Posterior capsular rupture
- Severe IOL optic tilt or decentration
- IOL dislocation out of the capsular bag
- Deposits on IOL
- IOL opacities
- Worsening of pre-existing macular edema or diabetic retinopathy

The following is a non-inclusive list of ADEs that are rare in incidence:

- Toxic Anterior Segment Syndrome (TASS)
- Hyphema
- Hypopyon
- Choroidal detachment/hemorrhage
- Thermal injury (i.e. phaco burn, corneal burn)
- Endophthalmitis
- Retinal detachment
- Loss of BCDVA ≥ 10 Early Treatment Diabetic Retinopathy Study (ETDRS) chart letters

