Appendix A: STUDY FLOW CHART

PROCEDURE/ASSESSMENTS	Preop Visit Day -60 to Day -1	Op Visit Day 0	Postop Visit 1 ^a 6 Hours ± 2 hours Postop	Postop Visit 2 24 Hours ± 4 hours Postop	Postop Visit 3 7 Days ± 2 days Postop	Postop Visit 4 30 Days ± 7 days Postop	Postop Visit 5 90 Days ± 14 days Postop
Informed Consent	X						
Demographic Data	X						
Medical History	X						
Urine Pregnancy Test	X	X ^b			X	X	X
Eligibility Criteria	X	X					
Randomization		X					
Fellow Eye Status	X						
Surgical Procedure ^c		X					
Manifest Subjective Refraction	X						X
Uncorrected Distance VA	X		X	X	X	X	X
Best Corrected Distance VA	X						X
Cataract Classification	X						
Slit Lamp Exam	X		X	X	X	X	X
Intraocular Pressure (Goldmann tonometry)	X		X	X	X	X	X
Fundus Exam (Dilated)	X						X
Ultrasound Pachymetry	X			X			X
ECD via specular microscopy of the central cornea	X						X
Concomitant Medications	X	X	X	X	X	X	X
Adverse Events ^d	X	X	X	X	X	X	X

^a Postoperative Visit 1 must occur on the day of surgery.

^b If last urine pregnancy test was more than 21 days after the preoperative visit, test should be repeated.

^c Required details of the surgical procedure are described in [Appendix C](#).

^d The period of collection of AEs starts from informed consent through study exit

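### Section 12.4.5 follows only UADEs to an endpoint, so the final outcome of any other SAE still open at study exit is not expressly required

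*Combined protocol and SAP*

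**What the plan says.** Section 12.4.5 contains two exit rules.

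- **AE rule.** Follow-up of an ongoing AE ends at the earliest of four limits. Three are resolution, no expected further change, and what standard of care dictates. The fourth, with a waiver attached, reads "or up to 30 days post final visit, whichever is shorter. Documentation in the CRFs of such follow-up is not required".
- **UADE rule.** Ongoing UADEs are followed by the sponsor and the investigator "until their medical endpoints are determined or until no further change in the condition is expected". No time limit is set.

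SAEs are not named in either rule. Section 12.4.1 gives the scope of the term: "adverse events include: ocular adverse events (AEs) in the study eye only; all ocular and non-ocular serious adverse events (SAEs", together with ADEs and UADEs. The same section defines an SAE as an AE that meets a seriousness criterion. A UADE is narrower. Apart from a catch-all for other unanticipated serious problems, the effect must be serious, be tied to the device, and be one that "was not previously identified in nature, severity or degree of incidence in the investigational plan or application".

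Reporting is covered in section 12.4.4. Every SAE goes on the AE CRF and on the SAE/UADE Report Form, and reaches the sponsor within 48 hours.

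On the collection period, section 12.1 says that the incidence and type of AEs "will be collected from the time the subject signs the ICF until study exit". Note d of Appendix A agrees: "The period of collection of AEs starts from informed consent through study exit".

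**The concern.** The trial is meant to document the safety of a new OVD against a marketed control. For a serious event, the question after its occurrence is how it ended: whether it resolved or left lasting impairment. Permanent impairment is itself one of the seriousness criteria in section 12.4.1.

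The dividing line in section 12.4.5 is whether an event was anticipated, not whether it is serious. A serious event that the plan foresaw, or one judged unrelated to the device, can leave the study open. Follow-up may then stop after at most 30 days, with no duty to enter what was found in the CRF. The safety report might then list the event as ongoing and be unable to say more.

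**Working it through.** No plan figure is in dispute. The check is a reading of the provisions against one another, plus one date calculation.

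**Step 1. Which rule covers an SAE that is not a UADE?** Two readings of AE in section 12.4.5 are possible.

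- *Broad reading*, following the definitions in 12.4.1: an SAE is a kind of AE, so the AE rule applies, with its 30-day limit and its CRF waiver.
- *Narrow reading*, following the labels in Tables 3 and 4, where AE marks the non-serious event and SAE the serious one: neither rule names such an SAE, so it has no exit rule.

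The final outcome is not required under either reading.

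**Step 2. Which SAEs are these?** Table 4 separates SAEs into non-device-related, device-related and anticipated, and device-related and unanticipated. Only the last group is a UADE. Section 12.4.1 names event types in two lists. One is introduced as "anticipated ADEs which have the potential of being considered as SAEs should the circumstances meet the necessary SAE criteria", the other by "The following is a non-inclusive list of ADEs that are rare in incidence". The second includes endophthalmitis, retinal detachment and TASS. Because the plan names these events, a serious case would generally not be a UADE, unless its severity or degree of incidence was not foreseen.

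**Step 3. Does another provision require the outcome?**

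| Section | What it provides | Does it require the final outcome? |
|---|---|---|
| 12.1; Appendix A, note d | AE collection until study exit | No |
| 12.4.4, Table 4; 12.4.4.1 | CRF entry, report form, 48-hour report | No follow-up or outcome report is stated |
| 12.4.4.3 | Further safety information if the sponsor asks | Only on request; placed under device deficiencies |
| 8.3.4 | As much data as possible before a subject is discontinued | Applies up to exit; afterwards care is outside the protocol |
| 11.2 | Post-study visits as necessary | Provides for visits, not for recording the outcome |
| 12.4.6 | Pregnancies followed to completion | Pregnancy only |

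**Step 4. When does the 30-day limit fall?** Visit 5 is at 90 ± 14 days (section 11.1, Table 2).

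- Earliest in-window visit: 90 − 14 = Day 76. Limit: 76 + 30 = Day 106.
- Latest in-window visit: 90 + 14 = Day 104. Limit: 104 + 30 = Day 134.

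The other three limits can only end follow-up sooner. An out-of-window Visit 5, which section 11.1.4 allows to be recorded as that visit, moves the date. A subject who exits early has an earlier limit, because the 30 days run from an earlier final visit. Early exit with an SAE is foreseeable: section 8.3 gives a non-ocular SAE as an example reason for withdrawal.

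As an illustration, take a retinal detachment found at a Visit 5 held on Day 90 and judged not to be a UADE. On the broad reading, follow-up may end by Day 90 + 30 = 120, and nothing learned after Day 90 need enter the CRF.

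**The case against.** The best defence has four parts.

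1. **The waiver may not reach SAEs.** Sections 12.4.1 and 12.4.2 also use AE, SAE, ADE and UADE as separate labels. This is a fair reading, but it replaces a weak exit rule with none.
2. **The outcome may be captured elsewhere.** The waiver concerns CRFs, while SAEs also go on the SAE/UADE Report Form, whose fields are not in the documents. Section 14.1 further requires compliance with device regulations and a good clinical practice standard, whose content cannot be checked here. This stands as a limit: the documents show that the outcome is not expressly required, not that it will be missing.
3. **The collection period concerns when events are found.** Sections 12.1 and Appendix A do not forbid updating an SAE already reported, and the sponsor, told within 48 hours, can ask for more. That is correct, but permission to update is not a duty to do so.
4. **Tiered follow-up is a legitimate choice.** So it is for non-serious events. Nothing in the plan explains why an anticipated serious event should have shorter follow-up than an unanticipated one.

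A reader might also infer more than the text supports. The two lists in 12.4.1 name 18 + 8 = 26 event types, and two of the three SAE groups in Table 4 lie outside the UADE rule. Those are counts of entries in the plan. They do not measure how many SAEs will be open at exit. Nor is a planned comparison lost, since section 13 plans no comparison of SAE outcomes between the arms.

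**Conclusion.** The point holds as a gap in safety data. For an SAE open at exit that is not a UADE, the plan either limits follow-up to 30 days and waives CRF documentation or, on the narrow reading, sets no exit rule. No provision expressly requires the outcome.

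Its size cannot be given as a number of cases, because the documents contain no rate of SAEs open at exit. What can be stated is the date range of Day 106 to Day 134 for an in-window Visit 5. The conclusion assumes that the SAE/UADE Report Form and its instructions do not already demand the final outcome. If they do, the recording gap closes and only the length of follow-up remains to be settled.

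It would be wrong to infer that SAEs go unreported or that patients are left without care. The event, its seriousness and the data up to exit are captured, and section 12.4.5 itself says that appropriate care continues. The IOP and ECD primary endpoints and their power are unaffected. The change is worth making because it is specific and cheap, not because the trial's conclusions are at risk.

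**What to change.** In section 12.4.5:

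- apply the existing UADE follow-up sentence to all SAEs open at exit;
- require the final outcome and its date, or the last known status at database lock, on the AE CRF or the SAE/UADE Report Form;
- keep the present rule for non-serious AEs.

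The cost is a wording change by amendment and one outcome entry for each SAE open at exit. The drawback is that a few SAE records stay open longer before lock. Allowing last known status at lock keeps that delay bounded.

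As an editorial matter only, sections 8.3.3 and 8.3.4 point to 12.4.4 and section 11.2 points to 12.4.6 for AE follow-up. All three should point to 12.4.5. These slips add no weight to the point.

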12.4.6 Pregnancy

All female subjects of childbearing potential must use an effective method of birth control during the course of the study, in a manner such that risk of contraceptive failure is minimized. Effective contraception is defined as stabilized on oral contraceptive for at least 3 months or use for 3 months of an intrauterine device (IUD), condom with spermicidal, diaphragm with spermicidal, implant, Nuvaring, injection, transdermal patch, and/or abstinence. Females on birth control pills must have taken the same type pill for at least three months prior to entering the study and must not change type during the study. Those who have not used birth control pills in the three months prior to being screened must not begin or resume usage during that period prior to entering the study. Abstinence is allowed as a birth control method.

Before enrolling a female subject of childbearing potential in this clinical trial, the investigator must review the following information about study participation:

- Informed consent requirements; and
- Contraceptives in current use.

Following review of this information and appropriate subject counseling, the investigator or designee and the subject must sign the informed consent before study enrollment.

During the study, all female subjects of childbearing potential are subject to urine pregnancy testing during their study visits and should be instructed to contact the investigator immediately if they suspect they might be pregnant (e.g., missed or late menstrual period).

If a subject or investigator suspects that the subject may be pregnant prior to study enrollment, the study product must be withheld until the results of laboratory pregnancy testing are available. If pregnancy is confirmed, the subject must not receive study product and must not be enrolled in the study.

Subjects who become pregnant during the study will be discontinued from the study and followed until completion of pregnancy. Pregnancy itself is not considered an AE.

All confirmed pregnancies must be immediately reported to the medical monitor and CRO contact within 48 hours of the investigator's awareness of the pregnancy. All confirmed pregnancies must be reported via confirmed facsimile or email transmission and must be submitted on a Pregnancy Report Form within 48 hours of the investigator's awareness of the pregnancy.

13 Statistics

Additional details of the statistical analysis will be provided in the SAP, which will be prepared and approved prior to database lock.

13.1 Study Endpoints

The following endpoints will be compared between the test and control groups.

13.1.1 Safety Endpoints

13.1.1.1 Primary Safety Endpoint

The primary safety endpoint will be the proportion of subjects who experience at least one IOP measurement ≥ 30 mmHg in the study eye at any follow-up visit. This endpoint will be evaluated cumulatively over all post-operative follow-up visits.

13.1.1.2 Secondary Safety Endpoints

- Mean change from baseline in IOP at the six hour post-operative visit
- Mean change from baseline in IOP at the 24 hour post-operative visit

13.1.2 Effectiveness Endpoint

13.1.2.1 Primary Effectiveness Endpoint

The primary effectiveness endpoint will be corneal ECD loss (%) from baseline to Postoperative Visit 5 (90 Days \pm 14 days) in the study eye.

13.1.2.2 Secondary Effectiveness Endpoints

There are no secondary effectiveness endpoints.

13.2 Hypotheses

13.2.1 Primary Hypotheses

13.2.1.1 Primary Safety Hypothesis

For the primary safety hypothesis test, the incidence of IOP observations at or above 30 mmHg refers to the number of study eyes experiencing one or more such events at any postoperative visit. Each subject will be classified as having experienced an IOP spike or not having experienced an IOP spike and will not be double counted. The safety null hypothesis (H_0) is that the test incidence (π_t) of IOP observations at or above 30 mmHg minus the control incidence (π_c) of IOP observations at or above 30 mmHg is greater than or equal to the non-inferiority margin (δ). The alternative hypothesis (H_1) is that the test incidence (π_t) of IOP observations at or above 30 mmHg minus the control incidence (π_c) of IOP observations at or above 30 mmHg is less than the non-inferiority margin (δ).

$$H_0: \pi_t - \pi_c \geq \delta$$

$$H_1: \pi_t - \pi_c < \delta$$

13.2.1.2 Primary Effectiveness Hypothesis

ECD loss will be evaluated from baseline to postoperative visit 5 (90 Days \pm 14 days) in the study eye. The primary effectiveness null hypothesis (H_0) is that the mean within-eye percent ECD loss with the investigational OVD (μ_t) minus the mean within-eye percent ECD loss with the control OVD (μ_c) is greater than or equal to the non-inferiority margin (δ). The alternative hypothesis (H_1) is that the mean within-eye percent ECD loss with the investigational OVD (μ_t) minus the mean within-eye percent ECD loss with the control OVD (μ_c) is less than the non-inferiority margin (δ).

$$H_0: \mu_t - \mu_c \geq \delta$$

$$H_1: \mu_t - \mu_c < \delta$$

13.2.2 Secondary Hypotheses

The secondary null hypotheses will be eligible for rejection only if both of the primary endpoints are met. As recommended in ICH E9, the nominal alpha risk will be 0.025 for the one-sided secondary superiority hypothesis tests.

The secondary hypotheses will be tested in two sequential families, with simultaneous testing of the hypotheses in the second family.

1. Family 1: Secondary Effectiveness Hypotheses
 - a. ECD loss superiority test
2. Family 2: Secondary Safety Hypotheses
 - a. IOP spike rate superiority test
 - b. Mean change from baseline in IOP at 6 hours post-op superiority test
 - c. Mean change from baseline in IOP at 24 hours post-op superiority test

The overall type I error for the secondary endpoint hypothesis tests in Family 2 above will be controlled by application of the Holm stepwise procedure.

13.2.2.1 Secondary Safety Hypotheses

13.2.2.1.1 IOP Spike Rate Superiority Test

The secondary safety null hypothesis regarding the IOP spike rate is that the test incidence (π_t) of IOP observations at or above 30 mmHg is greater than or equal to the control incidence (π_c) of IOP observations at or above 30 mmHg. The alternative hypothesis is that the test incidence is less than the control incidence.

$$H_0: \pi_t \geq \pi_c$$

$$H_1: \pi_t < \pi_c$$

If the null hypothesis is rejected then superiority will be claimed for the test OVD in the rate of IOP spikes.

13.2.2.1.2 Mean Change from Baseline in IOP Superiority Tests

Regarding the mean change from baseline in IOP at the six-hour and 24-hour post-op visits, the null hypothesis at each visit is that the mean change from baseline IOP for the investigational OVD group is greater than or equal to the mean change from baseline IOP for the control group. The alternative hypothesis is that the mean change from baseline IOP for the investigational OVD group is less than the mean change from baseline IOP for the control group.

$$H_0: \mu_t \geq \mu_c$$

$$H_1: \mu_t < \mu_c$$

For each of the visits, if the null hypothesis is rejected then superiority will be claimed for the test OVD in mean IOP.

13.2.2.2 Secondary Effectiveness Hypothesis

The secondary effectiveness null hypothesis is that the mean within-eye percent ECD loss with the investigational OVD (μ_t) is greater than or equal to the mean within-eye percent ECD loss with the control OVD (μ_c). The alternative hypothesis is that the mean loss with the investigational OVD is less than the mean loss with the control OVD.

$$H_0: \mu_t \geq \mu_c$$

$$H_1: \mu_t < \mu_c$$

If the null hypothesis is rejected then superiority will be claimed for the test OVD in ECD loss.

